4) Post-discharge support: At 24 to 48 hours post-discharge, a nurse Navigator will call the patient to assess the patient’s status, confirm receipt of and compliance with medications, verify the follow-up appointment schedule, assess for barriers to following the discharge plan, determine the need for a community health worker (CHW) referral, and review blood glucose control (patients who are discharged on non-insulin regimens will be expected to test their blood glucoses at least once a day, and patients who are discharged on an insulin regimen will be expected to test their blood glucoses at least twice a day). Similar phone calls will be made weekly for four weeks following discharge by a Navigator. If a patient reports significant high or low blood glucose levels, then the PI or a co-Investigator (Endocrinologists) will call the patient to adjust diabetes therapy (See Tables 1a and 1b for insulin dose adjustment protocols). Eligible patients will receive a referral for a nursing visit from a local home care agency to assess medical needs for support at home and medication reconciliation. Referral to a CHW may be made if subjects are found to have non-medical needs and/or obstacles to maintaining self-care and attending follow-up appointments. Such non-medical support might include transportation to and from medical appointments, food, housing, or legal assistance, relief from utility bills, verification of insurance, support groups and delivery of durable medical equipment.

Table 1a. **Outpatient basal insulin dose adjustment:**

Basal Insulin	
If mean FBG > 180 mg/dL for the last 2 consecutive days and no episodes of hypoglycemia	Increase daily basal dose by 4 IU
If mean FBG > 140 mg/dL for the last 2 consecutive days and no episodes of hypoglycemia	Increase daily basal dose by 2 IU
If mean FBG between 100 to 140 mg/dL for the last 2 consecutive days and no episodes of hypoglycemia	No Change
If any FBG between 70 – 99 mg/dl	Decrease by 4 IU or 10% of total daily basal dose
If any FBG < 70 mg/dl	Decrease by 8 IU or 20% of total daily basal dose
If any FBG < 40 mg/dl	Decrease total daily basal dose by 30%

FBG=Fasting blood glucose; Hypoglycemia=typical symptoms (e.g., sweating, tremor, acute hunger, anxiety) and/or blood glucose <70 mg/dL

Table 1b. **Outpatient prandial/pre-meal insulin dose adjustment based on subsequent mealtime/HS BG values:**

Pre-meal Rapid Insulin		
Pre-meal Dose, U	BG 70 – 100 mg/dl*	BG 141-180 mg/dl**

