≤ 10 U	Decrease by 1 U	Increase by 1 U
>11- 19 U	Decrease by 2 U	Increase by 2 U
≥ 20 U	Decrease by 3 U	Increase by 3 U
Pre-meal Dose, U	BG 40-70 mg/dl x 1	BG 180-240 mg/dl x 1

Readmission Pilot Trial

≤ 10 U	Decrease by 2 U	Increase by 2 U
>11- 19 U	Decrease by 3 U	Increase by 3 U
≥ 20 U	Decrease by 4 U	Increase by 4 U
Pre-meal Dose, U	BG < 40 mg/dl x 1***	BG > 240 mg/dl x 1
≤ 10 U	Decrease by 4 U	Increase by 3 U
>11- 19 U	Decrease by 6 U	Increase by 4 U
≥ 20 U	Decrease by 8 U	Increase by 5 U

Pre-meal insulin dose adjustment is based on the subsequent BG value, e.g., pre-breakfast insulin dose is based on the pre-lunch BG.

* If > ½ of the mealtime/HS BG values for the week were below target.

**If > ½ of the mealtime/HS BG values for the week were above target.

*** Decrease by 30-40% in the event of severe hypoglycemia (mealtime/HS BG < 40 mg/dl).

BG=blood glucose; Mealtime/HS=pre-lunch, pre-dinner, or bedtime

The above algorithm provides recommended insulin doses and may be modified based on clinical judgment of the investigator or co-investigator.

Usual care: Most aspects of the intervention go above-and-beyond usual care. Patients in the usual care group will receive the standard discharge instructions and medication reconciliation process. Those who are new to diabetes receive training by a floor nurse on using a glucometer as well as a stock set of printed educational materials. The floor nurses also train patients who are new to insulin injections as needed. Patients with diabetes are referred to outpatient diabetes education at Temple on a case-by-case basis as determined by the primary hospital provider team. Diabetes therapy upon discharge is decided on a case-by-case basis by the primary team. Discharge instructions are routinely sent to the primary care physician either by fax or EPIC. Most TUH patients receive a phone call 2 to 4 days after discharge from a CHW that includes checking on the status

Table 2. Timeline for assessments of subjects

Visit #	1	2	3	4	5	6	7	8
Time (weeks)	0	2 days	1	2	3	4	5	13
Intervention group								
Phone call/clinic visit								X
Psychometric assessments	X							X
Diabetes knowledge	X							X
30d endpoints								X
Interview							X	
A1C	X							X
Navigator call		X	X	X	X	X		
Blood glucose		X	X	X	X	X	X	
Adverse events		X	X	X	X	X	X	
Usual care group								
Phone call								X
Psychometric assessments	X							X
Diabetes knowledge	X							X
30d endpoints								X
A1C	X							X
Blood glucose								X

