Adverse events								X
Low-risk group								
Chart review/phone call								X
Psychometric assessments	X							X
Diabetes knowledge	X							X
A1C	X							X
30d endpoints								X

Readmission Pilot Trial

of follow-up appointments, confirming access to medications, and answering questions.

Data collection: The following data will be collected at baseline: A1c, sociodemographics, medical history, including HIV, substance abuse, and mental health status, which are likely risk factors for admission, relevant laboratory results, admission diagnoses, self-reported goals for health and diabetes, well-being (WHO-5), diabetes-related distress (PAID scale), perceived social support (MSPSS), perceived stress (PSS), diabetes knowledge (DKT2), depression screening by the PHQ-2/9, and health literacy by the BHLS (Table 2).

The following data will be collected during follow-up: A1c, discharge diagnoses, hospital readmission (date, primary diagnosis), ED visits (date, primary diagnosis), physician follow-up appointments scheduled and/or attended, post-discharge medication reconciliation (yes/no), cost of post-discharge care, self-monitored blood glucose levels, Nurse Navigator time to deliver the intervention (minutes), well-being (WHO-5), diabetes-related distress (PAID scale), perceived social support (MSPSS), perceived stress (PSS), diabetes knowledge (DKT2), depression (PHQ), and patient experience according to a brief questionnaire (**Appendix Item 3a [usual care] or 3b [intervention]**). These follow-up data will be collected during a phone call about 5 weeks after the index discharge. Baseline and 3-month post-discharge A1c levels will be obtained as part of standard-of-care. A letter reminding patients to do the 3-month blood draw for the A1c test will be sent by mail.

Data will be collected by phone interviews with subjects and review of the electronic medical record (EMR). The Research Specialist will be primarily responsible for screening and recruiting subjects, data collection and data entry.

Phase B: Qualitative evaluation of intervention

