In Phase B, in-depth individual interviews with intervention-group participants and the Navigators from Phase A will be conducted in-person to develop a better understanding of the intervention's acceptability, feasibility and effects. The interviews will be conducted between one and two months after the index discharge. These findings will provide critical information about the intervention to guide a future proposal for a definitive RCT. In addition to this formal qualitative work, the research team's experience with implementing the study will help refine the manual of procedures for the trial.

Study sample: Approximately 20 (maximum of 25) intervention-group participants in the Phase A pilot trial will be interviewed. The final sample size will be determined by achieving saturation of themes, the point at which no new information is being collected. This will be based on continual assessment by the investigators as the interviews are analyzed.[55] In the PI's prior study with a similar design (see Preliminary studies), 20 patients were included.[42]

Data collection and analysis: The PI will use an in-depth guide for semi-structured participant interviews that addresses the following topics: 1) the participants' experience in the intervention; 2) the acceptability of written materials; 3) barriers and facilitators to working with the Navigators and CHWs; and 4) suggestions for improving the intervention (**Appendix Item 4**). In a semi-structured interview, the interviewer uses the guide to address topics of interest and is encouraged to pursue relevant lines of questioning as they arise during the interview. Interviews will be conducted by the PI or research staff. Each interview will take about 30 to 45 minutes and will be recorded with a portable digital recorder. Hand-written observations and impressions during the interviews will complement the transcribed audio data. Thematic analysis will be used to identify common themes that reflect the underlying attitudes, values, and contextual constraints of participants in the intervention.[56, 55] Each interview will be coded by the interviewer then reviewed by the PI and research staff together to assure accuracy and consistency of coding. Initial codes will be standardized then organized into themes.

g) Data and Specimen Banking

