All participants will be given unique study identifiers. Data with personally identifiable information will be stored securely on HIPAA-compliant TUH servers. Data exported for statistical analysis will be stripped of personal identifiers. Participants will be free to withdraw from the study at any time.

Phase A: To minimize the risk of hypoglycemia, only patients with uncontrolled diabetes according to an elevated A1c will have their diabetes therapy adjusted. Patients will be followed closely for 30 days after discharge with weekly phone calls, and glycemic control will be monitored. Patients discovered to have hypoglycemia or hyperglycemia will be referred for adjustment of their diabetes therapy by the PI, an Endocrinologist.

A Data Safety Officer (DSO) not otherwise directly involved with the research, a senior diabetologist and clinical investigator with inpatient diabetes research experience, [name] at the University of Colorado Denver, will review de-identified data every 3 months. Adverse events will be reported to the Temple Institutional Review Board and the NIH according to standard policy.

Readmission Pilot Trial

Phase B: Every effort will be made to ensure that all qualitative data are kept confidential. The digital audio files produced will be used only for the purpose of this study. They will be downloaded from the recording device and stored on a secure computer in the research assistant's private GCRC office. The audio files will be transcribed. In the transcript, each subject will be assigned an anonymous study identification number. The data file linking personal identifiers and study identification numbers will be stored separately from the transcript data. The files with the transcribed data will have no personal identifiers and will contain no information linking an individual participant with their study code. The DSO will not monitor Phase B because there is minimal risk involved with this phase.

The following procedures will be implemented to ensure data safety and adequate monitoring:

- The PI will monitor study progress on an on-going basis and ensure the protection of human subjects, including the safe and secure collection and storage of data. An annual review will include assessment of accrual, adverse events, and data management practices.

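### In the intervention arm no adverse-event enquiry is scheduled after about week 5, although participation and the A1c outcome run to 3 months

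*Protocol*

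**What the plan says.** Several parts of the protocol bear on how long adverse events are sought in the intervention arm.

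- **Duration.** Section 8 d) has subjects in the study for 3 months after discharge, with the intervention delivered over the first 4 weeks and a final outcome assessment at 3 months. Section 8 e) item 15 is the A1c change from baseline to 3 months.
- **Calls.** Section 8 f), Post-discharge support, sets a Navigator call at 24 to 48 hours and then: "Similar phone calls will be made weekly for four weeks following discharge by a Navigator". Under Data collection: "These follow-up data will be collected during a phone call about 5 weeks after the index discharge".
- **The 3-month A1c.** "Baseline and 3-month post-discharge A1c levels will be obtained as part of standard-of-care". The only study action described for it is a mailed reminder.
- **Schedule.** In the table headed "Table 2. Timeline for assessments of subjects", the intervention arm's adverse-event row is marked at visits 2 to 7 (2 days to week 5) and is empty at visit 8 (week 13).
- **Safety monitoring.** Section 8 j) states: "Patients will be followed closely for 30 days after discharge with weekly phone calls, and glycemic control will be monitored". Section 9 says much the same and names hypoglycemia as the risk of the A1c-driven therapy changes.
- **Definition.** Section 8 j) counts as an adverse event any problem arising while the study runs that results from an assessment or from the intervention. It sets no 30-day or 5-week limit.
- **Later contact.** Phase B interviews: "The interviews will be conducted between one and two months after the index discharge". On numbers: "Approximately 20 (maximum of 25) intervention-group participants in the Phase A pilot trial will be interviewed".

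**The concern.** The study itself changes therapy at discharge for intervention subjects with A1c of 7% or more. Above 9%, home insulin may rise by 20 to 30% or basal insulin may be started. The protocol does not say that these regimens stop at week 4 or 5. Section 16 lets the research pharmacy supply diabetes medication throughout the study to intervention subjects who cannot afford it. Exposure to a study-directed regimen can therefore outlast the scheduled safety enquiry.

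The 3-month A1c change is the outcome that reflects therapy beyond 30 days. As planned, it would be read beside hypoglycemia sought only to about week 5. An admission for hypoglycemia at week 8 falls outside every 30-day endpoint. If related, it is a reportable serious adverse event, but nothing scheduled would bring it to the staff's notice. The pilot is meant to inform a definitive trial, and an analysis plan cannot recover events that were never collected.

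**Working it through.** The protocol gives no figure for this point, so the check sets the schedule beside the text and counts.

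**1. Do the table and the prose agree?**
- Table 2 time axis: 0, 2 days, then weeks 1, 2, 3, 4, 5 and 13 (visits 1 to 8).
- Adverse-event marks, intervention arm: visits 2 to 7 = 6; visit 8 = 0.
- Prose contacts: 1 call at 24 to 48 hours + 4 weekly calls = 5, matching the five Navigator-call marks. Adding 1 follow-up call at about week 5 gives 6.
- The six prose contacts fit the six marks. The blood-glucose row has the same pattern, and the text confirms that glucose is reviewed on the Navigator calls.

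**2. How long is the interval without scheduled enquiry?**
- 13 − 5 = 8 weeks; 8 / 13 = 62% of participation time.
- This is a share of calendar time only. The protocol does not give the share of hypoglycemia falling in those weeks.

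**3. Do the interviews close it?**
- Coverage: at most 25 / 60 = 42% of the intervention arm; at the planned 20, 20 / 60 = 33%. At least 60 − 25 = 35 subjects have no interview.
- Timing: two months is about 61 days; 61 / 7 = 8.7 weeks. That leaves 13 − 8.7 = 4.3 weeks before any week-13 contact.
- Content: the listed topics are experience of the intervention, written materials, barriers and facilitators to working with staff, and suggestions. Adverse events are not among them.

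**4. How many subjects are exposed?**
- Subjects with intensified regimens could number from 0 to 60. The protocol gives no basis for narrowing this.

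**5. What would record extraction cost?**
- Randomised subjects: 60 + 60 = 120.
- Assumed 3 to 10 minutes each: 120 × 3 = 360 minutes = 6 hours; 120 × 10 = 1,200 minutes = 20 hours.

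**The case against.** The case for leaving the plan alone has real force.

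- **Table 2 is doubtful at the week-5 and week-13 columns.** As read, it puts the psychometric scales and the 30-day endpoints at week 13, whereas the text places them at about 5 weeks. The text also never says at which calls adverse events are asked about. This stands, and it limits confidence. What remains is that the Navigator-call row agrees with the prose, the number of contacts fits, and no text anywhere schedules a later enquiry.
- **The window is a coherent choice.** The intervention lasts 4 weeks, enquiry continues about a week beyond it, the drugs are approved, and a primary care visit is confirmed. Attribution weakens once other clinicians can change doses. This lowers the weight of the point. It does not provide the late events that belong beside a 3-month A1c.
- **Late events have a route.** Reporting has no 30-day limit, the medical record is a stated data source, and the Data Safety Officer reviews every 3 months. True, but reporting and review depend on someone first learning of the event.
- **The stake is small.** The A1c change is the last of 15 secondary outcomes in a pilot that is not powered for outcome differences. No effect on a trial conclusion can be shown.

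A reader might infer that the 30-day statements in 8 j) and 9 contradict the 3-month study. They do not: they describe close clinical follow-up and glycemic monitoring, not the limit of adverse-event collection. A reader might also infer that the arms have different adverse-event windows, because the usual-care mark appears at week 13. The column of that mark is uncertain and no adverse-event comparison is planned, so the document does not support that claim.

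**Conclusion.** The point holds as a modest data-collection gap. In the intervention arm neither the text nor any Table 2 mark schedules an adverse-event enquiry after about week 5. Participation and the A1c outcome run to 3 months, and the adverse-event definition covers the whole study. Eight of 13 weeks have no scheduled enquiry, and interviews reach at most 42% of the arm without asking about harm.

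The conclusion assumes that the intervention arm's adverse-event marks are correctly read as ending at week 5; given the state of Table 2, confidence is medium. It does not claim that 62% of events would be missed, that late hypoglycemia is frequent, or that ending glucose collection at week 5 is wrong, since that fits its 30-day outcome. The weeks of active titration are covered, which keeps the severity low. The change is still worth making because it is cheap and uses an assessment the protocol already plans.

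**What to change.** At the 3-month final assessment, when the medical record is opened for the A1c, and even if no A1c was drawn:

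1. Extract dated ED visits and admissions for hypoglycemia since discharge, in both randomised arms.
2. Classify relatedness under the protocol's own adverse-event definition and pass related events to the Data Safety Officer.
3. Report counts to 30 days and to 3 months beside the A1c change.

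Table 2 appears to show a week-13 phone or clinic contact in the randomised arms, although the prose describes none. If that contact takes place, add one adverse-event question to it in both arms. Do not create a new call for this; that could mean up to 120 extra calls. Sections 8 j) and 9 can stay as they are.

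**Cost.** About 6 to 20 hours of record review by existing staff, on the assumed 3 to 10 minutes per subject.

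**Limits.** The counts are a lower bound, because events treated at home or at other hospitals are missed, and they may be small with at most 60 subjects per arm. Section 8 k) plans permission for continued record access after withdrawal only in the intervention group. Usual-care subjects who withdraw can be counted only to withdrawal unless the same permission is obtained from them.

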The proposed study will use the DERRI to identify diabetic patients at high-risk of readmission who will be provided with a novel intervention designed to reduce hospital utilization rates within 30 days of discharge. This multifactorial intervention builds on techniques effectively used in other inpatient populations, specifically, patient-centered discharge education, peri-discharge coordination of care, and post-discharge support by nurses and community health workers (CHWs), and adapts them to patients with diabetes.[2-8] In addition, the intervention includes adjustment of diabetes therapy upon discharge based on the admission A1c, which improves post-discharge glycemic control and is associated with a lower risk of 30d readmission.[9, 10]

Readmission Pilot Trial

We propose a pilot randomized controlled trial to address the following aims:

Aim 1: To explore the feasibility, acceptability, and efficacy of a novel multifactorial intervention designed to reduce all-cause readmission or ED visit rates within 30 days of discharge among hospitalized patients with diabetes who are identified as high risk based on the DERRI

Aim 2: To prospectively validate the readmission risk predictions generated by the DERRI

The usual care control group will provide the baseline risk of 30d post-discharge hospital utilization in the patient population predicted to be at high risk by the DERRI. Furthermore, we will prospectively follow patients who are predicted to be at lower risk to validate the DERRI in this population.

5) Background

Significance

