All data collected by the research team will be considered part of the participant's confidential record. Data collected on paper from research participants will be placed in a locked file cabinet in the GCRC within 24 hours. The destruction date of paper files will be at least 7 years from the termination of the study and will be authorized by the PI. Access to research and confidential records will be limited to clinical investigators and research coordinators.

h) Data Management

Statistical analysis: Distributions of the data will be assessed by descriptive statistical and graphical methods. To assess the randomization procedure, baseline values of all variables will be compared between the intervention and usual care group. Between-group differences for continuous variables will be compared using the Wilcoxon test. Proportions will be compared between groups using the chi-square test or exact tests when expected cell counts are less than 5. The primary outcome of 30d readmission rate will be compared between intervention and control groups with the chi-square test. Point estimates of 30d readmission rates will be obtained and presented with 95% confidence intervals. Time to readmission will be estimated by Kaplan-Meier curve and compared between groups by log-rank test. The composite of 30d readmission and ED visits will be compared by Cox regression model. Continuous secondary outcomes will be compared using Wilcoxon test. Categorical secondary outcomes will be compared using chi-square test. The primary analyses for all outcomes will be performed in the intention-to-treat (ITT) population. Secondary analyses for all outcomes will be performed in a per-protocol population restricted to subjects who complete at least one follow-up phone call. In addition, outcomes will be assessed for differences by the number of follow-up phone calls

Readmission Pilot Trial

completed (dose-response analysis). Lastly, all outcomes will be assessed in the ITT subgroup of subjects with a baseline A1c >7%. Statistical significance will be claimed at an alpha level of 0.05.

Power analysis: The sample size for Phase 2A was based on an expected drop-out and post-enrollment exclusion rate of 25% as well as the capacity of the research team. Because this is a pilot feasibility trial, the study is not powered to detect a difference in outcomes.

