- All data linking subjects to de-identified information will be maintained in a password-protected, encrypted computer with access limited to only those research personnel with a reasonable need to have such information.
- Reporting Adverse Events
 - Definitions:
 - Adverse Event: Any medical problem that manifests during the course of the study, as a result of an assessment or an aspect of the study intervention.
 - Serious Adverse Event: An adverse event that is fatal or life-threatening, results in significant or persistent disability, or requires hospitalization.
 - Unexpected Serious Adverse Event: Any event that has not been described in the protocol or informed consent document.
 - Reporting Mechanisms
 - All adverse events will be discussed at weekly operations meetings and reported to the PI and IRB according to standard operating procedure.
 - Serious adverse events (expected and unexpected) will be reported to the PI immediately and to the IRB in writing within 1 business day.
 - The NIH procedure for Reporting Clinical Study Serious Adverse Events will be followed for the reporting of expected and unexpected serious adverse events to the study sponsor.
- The DSO will review the protocol and study procedures every 3 months to ensure that proper regulatory processes are followed during study execution. In this role, he will:

Readmission Pilot Trial

- Review all adverse events or complications related to the study and make recommendations for protocol changes if indicated.
- Assure scientific integrity of the study by providing regulatory oversight.
- Assure participants' confidentiality and informed consent by reviewing study procedures.
- Provide advice, as requested, on quality assurance measures.

k) Withdrawal of Subjects

Subjects may withdraw at will at any time. Subjects may be withdrawn from the trial at the discretion of the PI due to a safety concern, if judged non-compliant with trial procedures, or pregnancy during the primary follow-up period (30 days after discharge). For subjects in the intervention group, we will obtain permission to continue to collect data from the electronic medical record.

9) Risks to Subjects

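### Section 8 k lets the PI withdraw subjects from the trial for undefined non-compliance, a ground that in the first 30 days falls almost only on the intervention arm and appears to end their 5-week follow-up call

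*Protocol*

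**What the plan says.** Section 8 k has one form of withdrawal, from the trial, and gives the PI the decision. Besides safety, the grounds are "if judged non-compliant with trial procedures, or pregnancy during the primary follow-up period (30 days after discharge". No criterion for non-compliance is given and no arm is named. The section does not separate stopping the intervention from leaving follow-up. Its next sentence reads: "For subjects in the intervention group, we will obtain permission to continue to collect data from the electronic medical record". It says nothing on whether the 5-week call continues, and nothing on records for a withdrawn usual-care subject.

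Elsewhere the protocol treats engagement as something to be measured:
- Aim 1 in section 4 is "To explore the feasibility, acceptability, and efficacy of a novel multifactorial intervention".
- Section 8 h states: "The primary analyses for all outcomes will be performed in the intention-to-treat (ITT) population".
- The per-protocol set in section 8 h is "restricted to subjects who complete at least one follow-up phone call".
- Section 8 h also plans a dose-response analysis, in which "outcomes will be assessed for differences by the number of follow-up phone calls" completed.

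Under post-discharge support in section 8 f, the intervention arm has a call at 24 to 48 hours and then weekly calls for four weeks. Subjects not on insulin are expected to test glucose at least daily, and "patients who are discharged on an insulin regimen will be expected to test their blood glucoses at least twice a day". For both randomized arms, the data collection paragraph of section 8 f puts the questionnaires, patient experience and outcome data in a phone call at about 5 weeks, supplemented by the electronic record.

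**The concern.** In a trial of feasibility and acceptability, a subject who ignores calls or does not test glucose is a result. Withdrawing that subject from the trial removes part of what Aim 1 sets out to observe.

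The ground is also unequal between the arms. A usual-care subject has almost nothing to fail inside the primary window. The PI or co-investigator sets and adjusts diabetes therapy in the intervention arm, so the person who judges compliance knows the allocation.

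If the least engaged intervention subjects lose the 5-week call, three things follow. Satisfaction and questionnaire scores in that arm come from the more engaged. The dose-response and per-protocol analyses lose 5-week outcomes for subjects whose low call count was partly fixed by a PI decision. Readmissions to other hospitals may be missed in one arm more than in the other.

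**Working it through.** **1. Which arm the ground can reach within 30 days**

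| | Intervention | Usual care |
|---|---|---|
| Study calls within 30 days | 1 + 4 = 5 | none described |
| Glucose testing expected by the protocol | daily, or twice daily on insulin | none described |
| About 5 weeks | follow-up call | follow-up call |
| 3 months | A1c | A1c |

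The early call that most usual-care patients get from a community health worker is described as routine care. Timing is taken from the text of section 8 f, because the column positions of Table 2 may have shifted in extraction. Section 8 k can be read with the 30-day limit on pregnancy alone or on all the grounds. If it limits all of them, usual-care subjects have virtually no procedure to fail. If it limits pregnancy alone, they can fail the 5-week call or the 3-month A1c, both after the primary window.

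**2. What a withdrawn intervention subject keeps**

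Section 8 k provides for record data, with permission. Records cannot supply the 5-week well-being, distress, social support, stress, knowledge and experience measures. If 5-10% of 60 are withdrawn, 3 to 6 subjects lack them.

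**3. Size for the primary outcome**

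The protocol gives no figure to reproduce. The calculation below assumes no true effect.

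Inputs from the protocol: 60 subjects in the intervention arm (section 8 c), and a 30-day readmission rate in diabetes of 14.4-21.0% (section 5; not specific to high-risk patients). The 25% allowance for drop-out and post-enrollment exclusion (section 8 h) is used only as a ceiling.

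Assumptions:
- *w*, the share of the arm withdrawn for non-compliance: 5%, 10%, 25%
- *r*, their readmission risk relative to the rest of the arm: 1, 1.5, 2
- *s*, the share of readmissions outside the Temple record: 10% to 40%
- withdrawn subjects would otherwise have answered the 5-week call and reported outside visits

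With true risk *p*, the risk in withdrawn subjects is p_w = r·p/(1 − w + w·r). With record-only follow-up, the observed rate falls by w·p_w·s.

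At p = 21%, 60 × 0.21 = 12.6 readmissions are expected in the arm.

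| w | r | p_w | Fall, s = 10% | Fall, s = 40% | Events missed of 12.6 |
|---|---|---|---|---|---|
| 5% | 1 | 21.0% | 0.05 × 0.21 × 0.1 = 0.1 points | 0.4 points | 0.06-0.25 |
| 10% | 1.5 | 0.315/1.05 = 30.0% | 0.10 × 0.30 × 0.1 = 0.3 points | 1.2 points | 0.18-0.72 |
| 25% | 2 | 0.42/1.25 = 33.6% | 0.25 × 0.336 × 0.1 = 0.8 points | 3.4 points | 0.50-2.02 |

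The extreme corner (w = 25%, r = 2, s = 40%) misses 1.4 of 8.6 events (2.3 points) at p = 14.4%, and 2.9 of 18 events (4.8 points) at an assumed high-risk rate of 30%. If the call is kept for every subject, the expected fall is 0.

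**The case against.** A reader might infer that withdrawn subjects drop out of the intention-to-treat analysis. On that reading the observed rate at p = 21% would be p/(1 − w + w·r). That is 0.21/1.05 = 20.0% (1.0 point low) for w = 10%, r = 1.5, and 0.21/1.25 = 16.8% (4.2 points low) for w = 25%, r = 2. The documents do not support this. Section 8 k keeps record data for the intervention arm, subject to permission, and section 8 h puts the primary analysis of every outcome in the intention-to-treat population. The detailed handling of withdrawn subjects may stand in an analysis plan that is not shown. Nor is there reason to assign the whole 25% allowance to non-compliance in one arm, since it covers all drop-out and post-enrollment exclusion.

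Other points on that side also stand:
- The clause is discretionary and covers every arm.
- Loss of the 5-week call is inferred from withdrawal from the trial combined with a record-only provision; it is not stated.
- The check for visits at other institutions is spelled out only for the low-risk group. For the randomized arms it is implied by phone interviews as a data source.
- Subjects who ignore Navigator calls may miss the 5-week call anyway, so the figures above are upper values for their inputs.
- Frequency of glucose testing is itself a secondary outcome, so some non-adherence is measured regardless.
- The record provision names only the intervention arm. A withdrawn usual-care subject could lose both call and record follow-up, which would push the bias the other way.
- The trial claims no power for a difference in outcomes.

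These points limit the size. They do not remove the conflict between an undefined ground for withdrawal from the trial and analyses that need poorly engaged subjects to be kept.

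**Conclusion.** The point holds in a limited form. The protocol itself fixes an undefined ground for withdrawal that in the primary window operates almost only in the intervention arm, is judged by someone who knows the allocation, and carries no stated follow-up beyond the record. This weakens intention to treat without undoing it.

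The effect on the readmission rate is probably small: about 0.1 to 1.2 points in favor of the intervention at 21% risk, for 5% withdrawn at equal risk up to 10% withdrawn at 1.5 times the risk. That is fewer than one event in 60. About 3.4 points needs 25% withdrawn, twice the risk and 40% of readmissions elsewhere. These figures rest on assumed values of *w*, *r* and *s*, on the call being lost, and on no opposing loss in usual care.

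The more direct loss is in the acceptability and feasibility results and the dose-response analysis, where the missing subjects are the least engaged. No flaw is shown in the safety and pregnancy grounds, and the point does not extend to them.

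**What to change.** In section 8 k, remove non-compliance as a ground for withdrawal from the trial. State instead that:
- non-compliance may end study procedures or the intervention only;
- such subjects stay in their assigned arm for the intention-to-treat analysis;
- they keep the scheduled 5-week call, the record review for outcomes and the 3-month A1c, in both randomized arms alike, unless they withdraw consent;
- each stop of the intervention, with its reason, is reported as a feasibility result.

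This settles follow-up and analysis only. When the intervention should stop remains for the investigators to decide.

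The cost is a short wording change and a few calls that are already scheduled (3 to 6 if 5-10% of 60 are concerned). Reported adherence and satisfaction may come out slightly lower. Whether the consent form also needs a change cannot be judged, because its pages are not in the copy reviewed.
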